## **Objectives**

### **Overall objectives**

To determine if timing of food consumption (daytime vs. delayed eating) affects body mass, adiposity, energy homeostasis, changes in circadian rhythms, cycling of gene expression, insulin sensitivity, and free fatty acid dynamics by enrolling 40 men and women with obesity without Metabolic Syndrome (a cluster of conditions-increased blood pressure, high blood sugar, excess abdominal body fat, and abnormal cholesterol or triglyceride levels-occurring together that increase the risk of cardiovascular disease and diabetes) in a randomized cross-over design study.

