## Accrual

Participants will be recruited through postings on campus and nearby workplaces, pamphlets to Penn Medicine practices, internet advertisements, and local media appearances. Participants will live/work within a 5 mi radius of the Hospital of the University of Pennsylvania for compliance with study visits and for ease of food delivery. UPenn currently employs 17,500 faculty and staff. Penn Medicine employs 21,626 people, and West Philadelphia (zip code 19104) has an adult population of about 54,718 (36% white, 40% black, 15% Asian; 50% female) (131). They will be required to have access to a personal electronic device for taking and sending photographs to study staff and receiving and responding to a link to REDCap (Research Electronic Data Capture) with daily queries regarding eating, sleep, and exercise parameters. We required this for our R21, and did not encounter issues; we expect this will not greatly impact recruitment. Power analysis for the outcome variables are based on our R21 data, which was designed to generate effect sizes (Cohens d; 127) for a R01 application; it uses the same study design sequence consisting of 2 orders (AB/BA design). Table 1 (see section C.1.) summarizes the power estimates, all assuming a 90% retention rate (n=36), a 2-sided paired t-test, and  $\alpha=0.05$  (G\*Power 3.1 program; 159). Power is above 80% for 7 of the 11 variables proposed, including weight, RQ, total cholesterol, triglycerides, insulin, trunk fat%/leg fat%, and circadian phase of leptin. Gene expression studies have not been done previously using our proposed design. However, within-subjects blood transcriptome studies in the circadian rhythm and obesity fields have detected gene expression changes using sample sizes of n=9-28 (84,90-92,94,95,98); similarly, within-subjects AT transcriptome studies in obese subjects have detected gene expression changes using sample sizes of n=6-20 (64,65,67,68). Thus, we anticipate having enough power to detect AT and blood expression changes (Specific Aims 2 and 3) between the daytime and delayed conditions using a within-subjects design and a sample size of n=36. Similarly, insulin sensitivity and free fatty acid dynamics studies have not been done previously using our proposed design. However, FSIGT studies have detected significant insulin sensitivity and free fatty acid dynamics changes using sample sizes of n=10-20 (121-123); thus, we anticipate having enough power to detect these changes (Specific Aim 3) between the daytime and delayed conditions using a within-subjects design and a sample size of n=36. Therefore, we will have sufficient power to detect significant differences between conditions in almost all of outcome variables for Specific Aims 1, 2 and 3, assuming a 10% study dropout rate (final sample size, n=36).

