
and disinhibition assessed by a subscale of the TFEQ (Maayan, 2011). The primary outcome is the interference score, which is calculated as RT (incongruent) minus RT (congruent) and measures the ability to suppress a habitual response in favor of an unusual one, controlling for speed of naming. The Delay Discounting Task\* (DDT) (Wileyto, 2004) is a measure of impulsivity that has been associated with obesity and eating behavior in numerous studies (Appelhans 2012, Dassen 2018, Klement 2018). In the DDT, participants choose between a smaller reward available immediately and a larger reward available after a longer delay. The immediate reward will be fixed and the magnitude and delay of the larger, later reward will vary from trial to trial. Participants will make 51 choices. The primary outcome will be the participants discount rate, which will be estimated by fitting a logistic regression that assumes a persons decisions are a stochastic function of the difference in subjective value between the two options (Wileyto, 2004). Keeping with standard behavioral findings (Kirby, 2003; Mazur, 1987), we will assume that subjective value (SV) is a hyperbolic function of the reward amount (A) and delay (D):  $SV = A/(1+kD)$ , where k is the participants discount rate. Larger values of k indicate a greater degree of discounting future rewards. A composite measure of cognitive inhibition will be calculated to be used in our analyses by averaging individual z-scores derived from the SST, Stroop interference score, and k-value. To eliminate time-of-day effects, we will administer the cognitive inhibition in the afternoon of the first day of each of the inpatient visits. These tasks take approximately 25 minutes to complete.

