**Analysis Plan**

**Overview** Our study proposes a within-subjects cross-over design. With a pre- and post- measurement for both eating conditions per participant for the outcomes, this design allows for comparisons within subject over time and between conditions. We will design our subject randomization on a two-treatment Latin Square design randomized for available subjects. This will allow us to include effects from the order of treatment (delayed eating first vs. daytime eating first) in the mixed effects model as a treatment order effect. **General Approach** The first phase of the analysis will be descriptive. The sample will be characterized by demographic variables (e.g., age, gender, race and ethnicity), health status (e.g., BMI and medical status) and behaviors (e.g., physical activity, dietary habits, sleep and eating timing). Categorical variables will be summarized by frequencies, while continuous variables will be summarized by the mean and 95% confidence intervals, median, standard deviation and range. The predictor of interest for each aim will be the eating condition (daytime vs. delayed). An analysis of data distributional properties will be performed to determine if variance stabilizing or normalizing transformations should be applied to the outcome measures as a function of eating condition. The second phase of the analysis will consist of model building and interpretation. For within-group outcomes, all available data will be used to estimate changes over time. Other fixed covariates in the models will account for chance imbalances (not balanced by randomization, such as subject) at the start of the study. Group-by-time interaction terms will estimate the differences in changes over time between the daytime and delayed eating condition on each continuous outcome of interest. Further analyses will adjust for departures from randomization related to dropout or suboptimal adherence (e.g., eating or sleeping outside the assigned time window, eating non-provided meals, exercising more than allowed). Thus, separate models will be generated for each of the outcome measures, with each outcome measure regressed on eating condition assignment, along with baseline outcomes and any other covariates deemed prognostic in preliminary analyses, including adherence measures such as sleep and eating timing, and exercise. Since there are two orders (daytime-delayed or delayed-daytime), clustering of participants will be modeled using a fixed covariate to indicate order. Assessments from individuals repeated over time are more alike than expected by chance and failure to consider the non-independence of assessments will yield misleading results due to the underestimation of variance. Mixed effects models with random intercepts and slopes for participants will account for the within-subjects correlation. Thus, we expect the linear mixed models to account for fixed treatment and order effects, and random subject effects. Missing data are sometimes handled by removing individuals with incomplete data from the analyses, a strategy that may potentially produce biased estimates such that those with complete data do not represent the original sample. The proposed analytic method (mixed effects models) assumes that data are missing at random (i.e., missing data are dependent only on observed, past values of covariates and outcomes), and these models use all available data. This approach will not account for informative dropout, where dropout occurs for reasons related to unobserved outcomes. Thus, sensitivity analyses will be run to estimate the potential impact of missing data on overall response to the daytime and delayed eating phases assuming that those with no measurements fared worse than those who remained in the study (151). Bias from non-compliance may also occur if participants do not adhere to the prescribed eating conditions. Non-compliance may be associated with outcomes and act as a confounder. To address this potential issue and estimate the effect of the eating conditions in the presence of full compliance, we will implement instrumental variable methods (152,153). All analyses for these 3 aims will be performed in the latest versions of the analytical software programs, SAS (v 9.3), Stata (v 13) and R (v 3.3.3). **Approach by Specific Aim** **Specific Aim 1.** The goal of this aim is to compare the daytime vs. delayed eating schedule on body mass (weight), adiposity, and energy homeostasis outcomes. We will fit separate linear mixed effect models for each outcome as described above. Baseline covariates that are found to be associated with missing data or unbalanced after randomization will be added to the models. Appropriate contrasts will be estimated with 95% CIs to quantify the difference between the daytime vs. delayed schedules in the reduction of outcomes. **Specific Aim 2.** The goal of this aim is to compare the daytime vs. delayed eating schedule on the phase changes in the circadian ghrelin and leptin rhythms and the phase and cycling of gene expression profiles from blood. Analysis of the circadian phase of hormonal and

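### The cognitive-inhibition composite z-scores the discount rate k on its natural scale; z-scoring ln(k) would be a cheap improvement to a measure outside the listed outcomes

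*Combined protocol and SAP*

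**What the plan says.** The Procedures section describes three computer tasks, each with its own main measure: stop-signal reaction time, the Stroop interference score and the delay-discounting rate. For the last it states: "The primary outcome will be the participants discount rate". The rate is estimated by a logistic regression fitted to 51 choices, under SV = A/(1+kD), "where k is the participants discount rate". The composite is then built "by averaging individual z-scores derived from the SST, Stroop interference score, and k-value". No transformation of k is named, and no mean or SD is given for the z-scores.

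The Analysis Plan (General Approach) provides for a look at distributions to decide "if variance stabilizing or normalizing transformations should be applied to the outcome measures as a function of eating condition". It does not mention k or the components of the composite, and it does not say whether a transformation would come before or after z-scoring.

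The composite is absent from the Primary and Secondary outcome variable sections and from the approach by specific aim. Accrual reports: "Power is above 80% for 7 of the 11 variables proposed, including weight, RQ, total cholesterol, triglycerides, insulin, trunk fat%/leg fat%, and circadian phase of" (the last item in its list is a leptin measure). The composite is not one of the seven variables named there.

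**The concern.** A z-score is a linear rescaling, so any skew in k passes unchanged into its component. If k has a long right tail, a few steep discounters supply most of that component's variance, and the condition contrast becomes noisier. Transforming the composite afterwards acts on the sum of three terms and cannot undo this.

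The protocol's own formula also suggests that k is naturally read in ratios. It enters only through the product kD, and value is halved at D = 1/k, since A/(1+1) = A/2. The same preferences can be expressed as the rate k or the delay 1/k. Z-scores of k and of 1/k give weight to different participants, whereas ln k and ln(1/k) differ only in sign.

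The missing reference mean and SD matters too. Standardising separately within each condition-by-time cell, which the text does not exclude, would set every cell mean to zero and erase the difference in change that the Analysis Plan sets out to estimate.

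**Working it through.** **The plan's own figure.** The trial plans its size "by enrolling 40 men and women with obesity without Metabolic Syndrome", with power calculations "all assuming a 90% retention rate (n=36), a 2-sided paired t-test, and" a significance level of 0.05. 40 × 0.90 = 36, which agrees with the stated n. No power, effect size or SD is given for k or the composite, so there is no stated figure to contradict.

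**Detectable effect.** For n = 36, a two-sided paired t-test at 0.05 and 80% power, the noncentral t distribution gives a standardised effect dz = 0.480.

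**Simulation.** There were 4,000 trials per setting, with 36 participants and four assessments each. The contrast was (post − pre) in one condition minus (post − pre) in the other, tested with a one-sample t-test. This stands in for the planned mixed-model interaction with complete data. Z-scores were pooled over participants and visits.

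Assumptions not in the documents:
- k is log-normal, with SD of ln k from 0.5 to 2.0.
- Within-person correlation is 0.5 or 0.7.
- The three tasks are independent.
- The effect acts on ln k.

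**Case A, all three tasks shift.** Each component gets dz = 0.480/√3 = 0.277, so the average of three independent components has dz = 0.277 × √3 = 0.480. Paired entries are for correlation 0.5 / 0.7.

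| SD of ln k | Share of raw-k sum of squares from the top 2 of 36 | Composite power, raw k (%) | Composite power, ln k (%) | Loss (points) |
|---|---|---|---|---|
| 0.5 | 0.30–0.33 | 78.8 / 78.5 | 79.8 / 80.6 | 1.0 / 2.1 |
| 1.0 | 0.47–0.52 | 73.6 / 71.7 | 79.0 / 79.6 | 5.4 / 7.9 |
| 1.5 | 0.65–0.69 | 67.3 / 64.5 | 78.4 / 79.5 | 11.1 / 15.0 |
| 2.0 | 0.78–0.80 | 63.9 / 59.4 | 80.8 / 79.6 | 16.9 / 20.2 |

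For ln k, the top two participants hold 0.19–0.22 of the sum of squares. The Monte Carlo standard error of each power figure is at most √(0.25/4000) = 0.8 points.

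**Case B, only k shifts (dz = 0.480 on ln k).** The composite then has dz = 0.480/√3 = 0.277, so its power is low on either scale.

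| SD of ln k | k alone, raw (%) | Composite, raw k (%) | Composite, ln k (%) |
|---|---|---|---|
| 0.5 | 78.6 / 77.4 | 34.4 / 33.3 | 34.4 / 34.8 |
| 1.0 | 65.3 / 58.3 | 27.0 / 26.5 | 34.2 / 35.2 |
| 1.5 | 43.0 / 38.2 | 18.0 / 18.0 | 33.5 / 35.6 |
| 2.0 | 27.2 / 23.8 | 13.8 / 13.9 | 33.7 / 36.2 |

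Analysed alone, ln k has 79–81% power throughout.

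**Type I error.** With no effect, the composite rejects in 3.8–5.7% of trials with raw k and 4.6–5.4% with ln k. Raw k tested alone rejects in 1.8–5.2%, so where it departs from 5% it is mostly on the low side.

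**The case against.** The strongest reply is that raw k is not a settled rule. The protocol calls the discount rate the outcome of its task, and the Analysis Plan has a distribution check for outcome measures, so an analyst could take logs of k before z-scoring and stay within the plan. That is right as far as it goes: the plan permits the better analysis. It does not require it or set the order of steps, and the literal instruction is to standardise k. The scale would be chosen after the data are seen.

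A second reply is that the skew is assumed. It is, and so is an effect acting on ln k. At SD 0.5 the loss is close to simulation noise.

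A reader might infer much larger damage from simulating k on its own. In a two-visit paired contrast with within-person SD of ln k 0.6 and a shift of 0.4, power is 79/79/77% on ln k but 44/26/16% on raw k, for between-person SDs of 1.0/1.5/2.0. Those figures describe neither the composite nor the planned contrast. The two-visit difference has SD 0.6 × √2 = 0.849 and dz = 0.4/0.849 = 0.47. The planned difference of changes has SD 0.6 × √4 = 1.2 and dz = 0.4/1.2 = 0.33. In the composite, k is one component of three, which dilutes the loss.

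It may also be said that taking logs is not free. That stands: the protocol states no positivity constraint on the fitted k, and a zero or negative estimate has no logarithm.

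**Conclusion.** The point holds as a cheap improvement of low importance. As written, the composite uses k untransformed, and the general transformation clause does not ensure otherwise. Under the assumptions listed, the cost to the composite is about 5 to 20 points of power for SD of ln k 1.0 to 2.0 when all three tasks respond. If only discounting responds, using ln k avoids a drop from about 34–36% to between 27% and 14% over the same SDs, but it does not make the composite adequately powered.

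A reader might go further and infer that the trial's stated power is wrong or that false positives are inflated. The documents support neither: they give no power figure for this measure, and the composite's error rate stays near 5%. The measure is in effect exploratory, and no listed primary or secondary outcome depends on it. That k is skewed in this sample cannot be established from the documents.

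**What to change.** State in the plan, before any condition contrast on these tasks is examined:

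1. The delay-discounting component is the z-score of ln(k), not of k.
2. How zero, negative and boundary estimates are handled. Fitting the choice model with ln k as the parameter removes negative values. A participant who always chooses the same kind of reward still has no finite estimate, so a bound is also needed, for example the smallest and largest k that the 51 choice pairs can distinguish.
3. All three components are standardised with one mean and one SD each, taken from the first baseline assessment over all participants and applied unchanged at all four visits.

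The cost is a short paragraph and a small change to the fitting and scoring code. No new data are needed. The downside is the boundary rule itself: without it, near-zero k would become an extreme low value on the log scale and replace one kind of outlier with another.

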
**The following documents are currently attached to this item:**

*There are no documents attached for this item.*

**Deception**

Does your project use deception?

No

**International Research**

Are you conducting research outside of the United States?

No

**Analysis Plan**

**Overview** Our study proposes a within-subjects cross-over design. With a pre- and post- measurement for both eating conditions per participant for the outcomes, this design allows for comparisons within subject over time and between conditions. We will design our subject randomization on a two-treatment Latin Square design randomized for available subjects. This will allow us to include effects from the order of treatment (delayed eating first vs. daytime eating first) in the mixed effects model as a treatment order effect. **General Approach** The first phase of the analysis will be descriptive. The sample will be characterized by demographic variables (e.g., age, gender, race and ethnicity), health status (e.g., BMI and medical status) and behaviors (e.g., physical activity, dietary habits, sleep and eating timing). Categorical variables will be summarized by frequencies, while continuous variables will be summarized by the mean and 95% confidence intervals, median, standard deviation and range. The predictor of interest for each aim will be the eating condition (daytime vs. delayed). An analysis of data distributional properties will be performed to determine if variance stabilizing or normalizing transformations should be applied to the outcome measures as a function of eating condition. The second phase of the analysis will consist of model building and interpretation. For within-group outcomes, all available data will be used to estimate changes over time. Other fixed covariates in the models will account for chance imbalances (not balanced by randomization, such as subject) at the start of the study. Group-by-time interaction terms will estimate the differences in changes over time between the daytime and delayed eating condition on each continuous outcome of interest. Further analyses will adjust for departures from randomization related to dropout or suboptimal adherence (e.g., eating or sleeping outside the assigned time window, eating non-provided meals, exercising more than allowed). Thus, separate models will be generated for each of the outcome measures, with each outcome measure regressed on eating condition assignment, along with baseline outcomes and any other covariates deemed prognostic in preliminary analyses, including adherence measures such as sleep and eating timing, and exercise. Since there are two orders (daytime-delayed or delayed-daytime), clustering of participants will be modeled using a fixed covariate to indicate order. Assessments from individuals repeated over time are more alike than expected by chance and failure to consider the non-independence of assessments will yield misleading results due to the underestimation of variance. Mixed effects models with random intercepts and slopes for participants will account for the within-subjects correlation. Thus, we expect the linear mixed models to account for fixed treatment and order effects, and random subject effects. Missing data are sometimes handled by removing individuals with incomplete data from the analyses, a strategy that may potentially produce biased estimates such that those with complete data do not represent the original sample. The proposed analytic method (mixed effects models) assumes that data are missing at random (i.e., missing data are dependent only on observed, past values of covariates and outcomes), and these models use all available data. This approach will not account for informative dropout, where dropout occurs for reasons related to unobserved outcomes. Thus, sensitivity analyses will be run to estimate the potential impact of missing data on overall response to the daytime and delayed eating phases assuming that those with no measurements fared worse than those who remained in the study (151). Bias from non-compliance may also occur if participants do not adhere to the prescribed eating conditions. Non-compliance may be associated with outcomes and act as a confounder. To address this potential issue and estimate the effect of the eating conditions in the presence of full compliance, we will implement instrumental variable methods (152,153). All analyses for these 3 aims will be performed in the latest versions of the analytical software programs, SAS (v 9.3), Stata (v 13) and R (v 3.3.3). **Approach by Specific Aim** **Specific Aim 1.** The goal of this aim is to compare the daytime vs. delayed eating schedule on body mass (weight), adiposity, and energy homeostasis outcomes. We will fit separate linear mixed effect models for each outcome as described above. Baseline covariates that are found to be associated with missing data or unbalanced after randomization will be added to the models. Appropriate contrasts will be estimated with 95% CIs to quantify the difference between the daytime vs. delayed schedules in the reduction of outcomes. **Specific Aim 2.** The goal of this aim is to compare the daytime vs. delayed eating schedule on the phase changes in the circadian ghrelin and leptin rhythms and the phase and cycling of gene expression profiles from blood. Analysis of the circadian phase of hormonal and

amplitude and phase of expression data will use linear mixed effects cosinor analysis (154), which accounts for systematic inter-individual differences. We will fit separate linear mixed effect models for ghrelin and leptin phases as described above. For transcriptomics, gene expression count data will be normalized in R using the TMM function in edgeR (155) and voom in the limma package (156). We will use linear mixed effect models against RNA-seq depth count data to test the differences in genes between the daytime and delayed conditions. Mixed model analysis will be done on the normalized RNA count data to adjust for effects such as condition order and random subject effects using the lme4 package (157) in the R statistical environment version R-3.2.3. P-values for each test will be generated from the lmer results using the Anova function in the R car package (158). Coefficients of the lme analyses will represent the log2 fold change between the two conditions tested (change in daytime vs. change in delayed). We will use a p-value cutoff adjusted by false discovery rate of 0.05 to detect all RNA changes of statistical significance comprehensively. Pathway analysis will be run in various functional enrichment analysis tools, e.g., Metacore (Thomson Reuters) and Ingenuity Pathway Analysis software (Qiagen). We also will cluster genes by phase for each of the 4h sample bins and compare them with circadian rhythm hormone phase profiles using correlational analysis to identify how different blood markers are related as a function of eating condition; this may allow for identification of additional genes implicated in timed eating. Each phase cluster can also be analyzed for statistical significance of enrichment against a number of biological pathways and gene sets. Specific Aim 3. The goal of this aim is to compare the daytime vs. delayed eating schedule on insulin sensitivity and free fatty acid dynamics and on AT gene expression. Changes in insulin sensitivity and free fatty acid dynamics by condition will be compared with linear mixed-effects models. Statistical analysis of gene expression data will be conducted as described for Specific Aim 2. As AT and blood will be collected on the same day, we will also compare pre-post changes in AT and blood expression using meta-analyses, to identify how different tissues relate to each other as a function of eating condition. This will also allow indirect comparison of hormonal data with AT gene expression. Finally, we will correlate AT gene expression with fasting lipid and glucose levels.

The following documents are currently attached to this item:

*There are no documents attached for this item.*

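### The outcome-model sentence allows post-randomisation adherence covariates, chosen from the data, into the Aim 1 and ghrelin/leptin phase models, and no adherence-free model is named as primary

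*Combined protocol and SAP*

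**What the plan says.** All of this is in the Analysis Plan of the combined protocol and SAP.

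- **The model sentence (General Approach).** A separate model is planned for every outcome measure. It contains assigned condition, the baseline outcome and "any other covariates deemed prognostic in preliminary analyses, including adherence measures such as sleep and eating timing, and exercise".
- **Who inherits it.** Specific Aim 1 covers weight, adiposity and energy homeostasis, which are also the protocol's primary outcomes. It states: "We will fit separate linear mixed effect models for each outcome as described above". Specific Aim 2 refers back in the same way for ghrelin and leptin phase.
- **Text pointing to a main model without adherence terms.** Before adherence is mentioned, the plan says "Other fixed covariates in the models will account for chance imbalances" at the start of the study, and "Group-by-time interaction terms will estimate the differences in changes over time between the daytime and delayed eating condition". The sentence just before the model sentence reads "Further analyses will adjust for departures from randomization related to dropout or suboptimal adherence". The later summary is "we expect the linear mixed models to account for fixed treatment and order effects, and random subject effects". Aim 1 itself names only baseline covariates: "Baseline covariates that are found to be associated with missing data or unbalanced after randomization will be added to the models".
- **Non-compliance.** To estimate the effect under full compliance, "we will implement instrumental variable methods".

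None of these passages calls any model primary.

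**The concern.** Under Procedures, randomisation follows the baseline assessment. Daily queries, logs and actigraphy then record eating, sleep and exercise during each condition. Adherence is therefore a post-randomisation variable. Eating timing is the intervention itself, and sleep and exercise may respond to the assigned schedule.

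The plan also lets covariates enter according to what looks prognostic in preliminary analyses. Two analysts could both follow the plan and report different condition effects on weight, body composition, resting energy expenditure and fuel oxidation. One would have adjusted for adherence and the other not, with the choice made after seeing data.

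**Working it through.** **1. The plan's own figure.** Under Accrual, 40 enrolled with 90% retention gives 40 × 0.90 = 36, which reproduces. The stated power for 7 of 11 variables cannot be recomputed, because the Table 1 effect sizes are not in the text. For n=36, a two-sided paired t-test and alpha 0.05 (all from Accrual), the noncentral t distribution gives 80% power at d = 0.480.

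**2. Where adherence does no harm.** Take the pre/post model whose estimate is (post − pre under daytime) − (post − pre under delayed). A per-condition adherence summary X has the same value at pre and post. Its contribution to each change is therefore bX − bX = 0, and it drops out of the contrast. A numerical check used n=36, four assessments, random intercept and slope, and departures differing by 0.5 h between conditions. Over 40 simulated datasets the estimates with and without X differed by at most 1e-14, with the standard error essentially unchanged. This holds for complete data and no adherence-by-time term.

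**3. Where it can do harm.** The model sentence can also be read as a regression of post values or changes with the baseline outcome as a covariate. X then does not cancel. The same is true if adherence is time-varying or interacted with time.

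**4. Illustration for case 3.** The paired outcome difference is regressed on the paired difference in departure from the assigned window, and the intercept is the condition effect.

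Assumed inputs, none from the documents:
- true effect d = 0.48
- per-condition SD of departure 0.5 to 1.0 h
- within-person correlation r of departure across conditions, 0 or 0.5
- mean between-condition difference in departure m = 0, 0.25 or 0.5 h
- shared-cause correlation rho with the outcome difference, 0.1 to 0.3, for the shift

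Formulas:
- s = SD × √(2(1 − r))
- SE ratio = √(1 + m²/s²), with no shared cause
- shift = rho × m/s, in SDs of the paired outcome difference, in either direction

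Example: m = 0.5, SD = 0.5, r = 0.5 gives s = 0.5 × √1 = 0.5. The SE ratio is √(1 + 0.25/0.25) = 1.414. With rho = 0.3 the shift is 0.3 × 0.5/0.5 = 0.30, and 0.30/0.48 is about 62%.

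| m (h) | r | SE ratio, SD 1.0 to 0.5 h | Power, SD 1.0 to 0.5 h (rho = 0) | Shift (SD units) | Shift as % of 0.48 |
|---|---|---|---|---|---|
| 0 | – | 1.01 (simulated) | 79% | 0 | 0 |
| 0.25 | 0 | 1.016 to 1.061 | 78% to 74% | 0.018 to 0.106 | 4 to 22 |
| 0.25 | 0.5 | 1.031 to 1.118 | 76% to 69% | 0.025 to 0.150 | 5 to 31 |
| 0.5 | 0 | 1.061 to 1.225 | 74% to 62% | 0.035 to 0.212 | 7 to 44 |
| 0.5 | 0.5 | 1.118 to 1.414 | 69% to 50% | 0.050 to 0.300 | 10 to 62 |

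Power comes from 20,000 simulated trials per setting. Shifts run from rho 0.1 at SD 1.0 h to rho 0.3 at SD 0.5 h. The power and shift columns should not be combined, since one assumes no shared cause and the other requires it.

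**The case against.** **The adherence-adjusted models are already supplementary.** The model sentence directly follows the one on further analyses and may simply describe them. Several other statements point to an adherence-free main model. This is a reasonable reading and may be what the investigators intend. For that reason, a reader who inferred that the plan makes an adherence-adjusted model its main analysis would go too far: entry is permitted, not required. But the model sentence covers every outcome measure and is the fullest statement of the regression. Aim 1 adds baseline covariates without removing anything, and the treatment, order and subject summary does not exclude other terms.

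**Adjustment need not bias anything.** A reader might infer that conditioning on any adherence measure necessarily changes the condition effect. Step 2 shows that it does not under the plan's group-by-time estimator, with complete data and a per-condition, non-interacted term. This part of the objection stands in full.

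**The numbers are assumed.** Also correct. They come from a simpler model than the planned four-assessment mixed model, and the largest are corner cases. A reader might reach far worse figures by entering eating timing as clock time, since the windows are 4 h apart. The daily query about eating outside the assigned window, and the plan's own description of poor adherence, point instead to window-relative coding. Daily queries and same-day staff contact aim to keep departures small, and nothing in the documents shows that they differ between schedules.

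**Instrumental variables already deal with non-compliance.** They target the full-compliance effect. They neither name a primary model nor take adherence out of the others.

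**Adjustment has a scientific purpose.** Background sections A.3 and A.6 aim to isolate meal timing with sleep and exercise controlled. That supports keeping these analyses as supplementary ones.

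**Conclusion.** The point holds as a fault in the stated covariate rule that should be fixed. The plan permits post-randomisation covariates, selected from the data, in the models for the primary outcomes and for ghrelin and leptin phase, and it designates no adherence-free primary model. It does not hold as a claim that the planned condition effect is biased.

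Bias and loss of precision arise only if adherence enters a model of post values or changes adjusted for the baseline outcome, or enters as a time-varying or time-interacted term, and departures differ between conditions. Bias in the illustration also needs a cause shared with the outcome. On the assumed inputs the effect runs from negligible (similar departures) to the corner values in the table, which are neither estimates nor bounds for this trial.

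The point does not extend to gene expression, which has its own specification without adherence terms. Nor does it extend with confidence to insulin sensitivity and free fatty acids: Aim 3 has no such back-reference, although the general wording about each outcome could be read to reach them.

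**What to change.** In the General Approach:

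1. State that the primary models for Aim 1 and for ghrelin and leptin phase contain assigned condition, the group-by-time term, order, random subject effects, and only baseline or pre-condition covariates.
2. Move the adherence-measure phrase out of the model sentence and into the sentence on further analyses. Moving it, rather than deleting it, keeps the specification of those analyses.
3. Label the adherence-adjusted models and the instrumental-variable analysis as supplementary, and state how each adherence measure is coded and entered.
4. Date the change before outcomes are compared by condition. At this version 32 of the planned 40 participants were already enrolled.

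The cost is analysis-plan wording only. No new data are needed and no planned analysis is lost.
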